- A description of the subject selection criteria and rationale for selection in terms of the scientific objectives and proposed study design;
- A compelling rationale for proposed exclusion of any sex/gender or racial/ethnic group;
- Justification for the inclusion of vulnerable groups such as children, prisoners, adults with impaired consent capacity, or others who may be vulnerable to coercion or undue influence.

Please consider these resources:

[NIH Diversity Policy](#)

[FDA Diversity Guidance](#) ⓘ

Pilot study

Inclusion criteria. Potential participants will be healthy controls who are employed in and around [name]. For inclusion in the pilot, they need to be 1) 18-55 years of age; 2) male or female gender 3) Able to read, understand and communicate in English; 4) Can have a past/current history of smoking.

Exclusion criteria. Intoxication with substances on day of the study.

Study Proper

Inclusion criteria. Potential participants will be: 1) Patients enrolled in the Bluegrass Clinic; 2) 18-55 years of age; 3) male or female gender 4) Able to read, understand and communicate in English; 5) willing to adhere to the general rules of the Bluegrass Clinic/SMARTClinic/Beyond Birth Clinic; 6) willing and able to abstain from drug use other than Suboxone; 7) exhaled breath on day of study CO < 5 ppm; 8) Stabilized on maintenance buprenorphine if having comorbid opioid use disorder.

Exclusion criteria. Traumatic brain injury, history of seizure disorder, history of or current diagnosis of schizophrenia, intracranial metal shrapnel, previous adverse effect with TMS, sub-threshold consistency while performing behavioral tasks, failure to show baseline attentional bias to smoking versus neutral cues.

We will exclude pregnant females in our study due to danger of MRI radiation to the unborn fetus.

The main study is not connected to the Bluegrass HIV clinic, SMART clinic or the Beyond Birth Clinic. A person can be enrolled and receiving care at these clinics, and their participation in the research project does not impact their standing in any of these clinics. Participation is truly voluntary in nature.

Attachments

Indicate the targeted/planned enrollment of the following members of minority groups and their subpopulations. Possible demographic sources: [Census Regional Analyst Edition](#), [Kentucky Race/Ethnic Table](#), [Kentucky Population Data](#).

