Study Proper. This will be a double blind randomized controlled trial. All subjects will receive both TBS and sham TMS in a randomized manner with counter balancing. The TBS session and sham TMS will be done on separate days. Subjects will be randomized to receive either TBS first and sham TMS second, or sham TMS first and TBS second. The PI ([name]) will be blind to the randomization status and will supervise the TMS session. Subjects will also remain blind to the randomization status. This will be facilitated by the Magventure Active/sham TMS coil which has been shown to maintain integrity of blinding in subjects regarding group assignment. We will recruit 30 patients from one of these clinics - the Bluegrass Clinic, SMART clinic in psychiatry and Beyond Birth Clinic in Psychiatry. All of them would receive TBS and sham TMS on separate days. The Bluegrass HIV clinic has a closely monitored population of PLWHA patients. The PI ([name]) and a research assistant would interface with [name] at the Bluegrass HIV Clinic on a weekly basis and with [name] on a daily basis to recruit patients for this study. The PI ([name]) and the research assistant will also interface with [name] (who heads the SMART clinic and Beyond Birth Clinic) on a weekly basis. If interested in participating, we will provide subjects with information and seek informed consent before proceeding with the study.

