For the study proper, we will recruit 30 subjects from the Bluegrass HIV Clinic, SMART clinic and Beyond Birth Clinic. Study members will interface with all providers in these clinics on a daily basis. All providers in these clinics will be provided multiple copies of the study flyer. All providers in these clinics will also be informed about inclusion and exclusion criteria for the study, based on which all patients will be screened by them. The PI ([name]) and a research assistant will interface with a contact in each of these clinics on a daily basis. Business cards (that list a few study details and a call back number if subjects are interested in the study) will be provided to subjects at each of these clinics by clinic providers. The case manager for this clinic [name] will send an email to all patients from the clinic, with the study flyer attached and informing them about the study. Subjects interested in the study can call the number provided on the business card to express interest in the study. This number belongs to the PI ([name]). He or the research assistant will administer a phone script to subjects who call back to assess subjects' suitability for the study. Once a subject is identified as suitable for the study, they will be asked to meet [name]/research assistant at [name] to get informed consent if they are interested in study participation and fulfill other eligibility criteria for the study. This process will also encompass MRI screening, examining urine drug screen and breathalyzer results. Following this step, patients will be randomized to either the treatment arm or sham arm by study co-investigator [name]. Half of compensation for study participation would be provided prior to starting the study and rest of it at study completion. All data collected from phone screening would be entered into RedCap, regardless of whether subjects do or don't fulfill inclusion and exclusion criteria.

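### Eligibility admits only patients of the HIV clinic, but recruitment runs through three clinics, so either some recruits are ineligible or subjects without HIV can enter

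*Combined protocol and SAP*

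**What the plan says.** The sample of the study proper is described in several places.

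- **Subject Demographics, Study Proper.** There are eight inclusion criteria. The list opens "Potential participants will be: 1) Patients enrolled in the Bluegrass Clinic; 2) 18-55 years of age". Criterion 5 asks that subjects be "willing to adhere to the general rules of the Bluegrass Clinic/SMARTClinic/Beyond Birth Clinic". Criterion 7 is "exhaled breath on day of study CO < 5 ppm". One exclusion is "failure to show baseline attentional bias to smoking versus neutral cues". A closing paragraph says "A person can be enrolled and receiving care at these clinics" and that taking part does not affect their standing there.
- **Study Design.** "We will recruit 30 patients from one of these clinics - the Bluegrass Clinic, SMART clinic in psychiatry and Beyond Birth Clinic in Psychiatry".
- **Subject Recruitment Methods & Advertising.** For the study proper, "we will recruit 30 subjects from the Bluegrass HIV Clinic, SMART clinic and Beyond Birth Clinic". Providers in these clinics are to be "informed about inclusion and exclusion criteria for the study, based on which all patients will be screened by them". Flyers listing the criteria go to providers at three clinics.
- **Resources.** Bluegrass is an HIV service with 1700 patients, all PLWHA. SMART is a programme for substance use disorders, and HIV is not mentioned. Beyond Birth's patients are not described.
- **Records, Privacy, and Confidentiality.** The chart is screened before recruitment for seizure disorder and schizophrenia. The paragraph on headaches and withdrawal refers to each subject's own clinic and lists the three as alternatives.
- **HIV/AIDS Research.** Subjects are described as having an HIV diagnosis, and HIV testing is ruled out.
- **Title, background and benefits.** All three name PLWHA as the population. The benefits text speaks of smokers with HIV, and Aim 2 (Objectives) is worded for smokers.

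**The concern.** The eligibility list and the recruitment text describe different source populations for the same 30 subjects. Membership of the Bluegrass clinic is the only listed criterion that implies HIV, so whether it applies to everyone decides whether this is a sample of people with HIV.

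Two things are at stake. The first is eligibility: a provider at SMART or Beyond Birth who screens on the list as written must turn away anyone not also enrolled at Bluegrass, although the plan sends that provider flyers and cards in order to recruit. The second is inference: if criterion 1 is set aside for those clinics, the sample may be mixed in HIV status, while the title, background and benefits text speak of PLWHA.

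A smaller gap of the same kind concerns smoking. The aims presume smokers, but the inclusion list does not ask for them.

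**Working it through.** The plan gives no figure to reproduce on this point, so the check is a comparison of texts.

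**Step 1. Source of subjects.**

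| Place | Source clinic(s) |
|---|---|
| Subject Demographics, criterion 1 | Bluegrass only |
| Subject Demographics, criterion 5 | rules of all three |
| Study Design | one of the three |
| Subject Recruitment Methods & Advertising | all three; providers at each screen patients and receive flyers |
| Records, Privacy, and Confidentiality | each subject's own clinic, one of three |

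Criterion 5 alone would not show a conflict, because it concerns clinic rules rather than recruitment. The conflict is between criterion 1 and the Study Design and recruitment texts.

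**Step 2. If criterion 1 governs.** HIV is implied by enrolment at Bluegrass. A SMART or Beyond Birth patient who is not enrolled at Bluegrass is ineligible, and recruitment through those clinics can yield only patients enrolled at both.

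**Step 3. If the recruitment text governs.** Then something else must secure HIV status. Going through the candidates:

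- Inclusion criteria 2 to 8: age, sex, English, clinic rules, abstinence from drugs, exhaled CO, and stabilisation on buprenorphine where opioid use disorder is present. None names HIV.
- Exclusion criteria: none names HIV.
- Chart screen in Records, Privacy, and Confidentiality: seizure disorder and schizophrenia, not HIV.
- HIV/AIDS Research: states the diagnosis as a fact about the subjects and rules out testing.
- Data collected: the Records section includes other medical illnesses and medication history. HIV status might be found there, but as data, not as an entry rule.

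On this reading a person without HIV meets every listed criterion.

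**Step 4. Number affected.** Neither Study Design nor the recruitment section allots a number of subjects to each clinic, and HIV prevalence at SMART and Beyond Birth is not given. The documents support no estimate.

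**Step 5. Smoking.** None of the eight inclusion criteria mentions it. The CO criterion is an upper limit, which a non-smoker also meets. The attentional-bias exclusion bears on smoking only indirectly and has no stated cut-off. The pilot is meant to show that this measure differs between smokers and non-smokers (Objectives), so the exclusion cannot yet stand in for a smoking criterion.

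**Step 6. Effect on the comparison.** Each subject receives both TBS and sham, in randomised order. HIV and smoking status do not differ between the two conditions within a subject, so a mixed sample does not bias the contrast. It changes whom the contrast describes.

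**The case against.** **Dual enrolment.** Criterion 1 and the recruitment text agree if every subject is a Bluegrass patient and some are also treated, and approached, at SMART or Beyond Birth. The sentence on receiving care at these clinics, criterion 5, the allowance for opioid use disorder in criterion 8, and the HIV/AIDS Research statement all fit this. The Study Design phrase about one of the clinics could mean the place of approach. This reading is possible but unlikely, because the Records section assigns each subject to one of three clinics. If it is intended, the plan does not say so, and a screening provider could not tell.

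**Intention is clear elsewhere.** The title, background, benefits and HIV/AIDS Research texts all point to people with HIV. Aim 2, the benefits text and the attentional-bias exclusion point to smokers, and a same-day CO ceiling makes most sense as an abstinence check in smokers. This stands as evidence of intention and makes the smoking gap mainly one of missing detail. It does not supply an entry rule.

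**Unseen documents.** The phone script, pre-screening form, consent form, flyer and attached protocol are not available here and may ask about HIV or smoking. This limits what can be said about the actual sample. It does not remove the conflict between two current texts.

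**Timing.** The file is marked closed, and its continuing-review section gives a total of 10 enrolled. If no one else will enter, changes to recruitment wording come too late, but reporting status and limiting the conclusion remain possible.

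**Conclusion.** The contradiction is in the current text, and confidence in it is high. Either SMART and Beyond Birth recruits not enrolled at Bluegrass are ineligible, or people without HIV can enter. Confidence that the enrolled sample is actually affected is moderate: the number is unknown, unseen screening forms may close the gap, and dual enrolment is not excluded. The missing smoking criterion is secondary.

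Three stronger readings are tempting, and the documents do not support them.

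- A reader might infer that the trial cannot support any statement about PLWHA. A possibly mixed sample only limits such statements to the subjects who have HIV.
- A reader might apply the 70% smoking rate that Resources gives for Bluegrass to 30 subjects and predict a count of non-smokers. The plan does not propose unselected sampling of that clinic, and it gives no smoking rate for the other two.
- A reader might infer that the TBS-sham comparison is invalid. It stays valid within subject; only the population it describes is in question.

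**What to change.** Reconcile criterion 1 with Study Design and with both recruitment statements (source clinics and flyers), in one of two ways.

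1. **Keep the HIV population.** Require a chart-documented HIV diagnosis for every subject, whichever clinic refers them, and add HIV to the chart screen in Records, Privacy, and Confidentiality. Cost: wording, one chart item, and a smaller eligible pool at SMART and Beyond Birth.
2. **Keep the three clinics.** Name all three in criterion 1, record HIV status as an explicit field, restate the population in the title and aims, and limit PLWHA statements to subjects with HIV. Cost: wording, one data field within information already collected, and a narrower PLWHA conclusion.

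If dual enrolment is what is meant, criterion 1 and Study Design should say so.

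For smoking, list current smoking as a numbered inclusion criterion if the phone script or forms already apply it, so that the provider screen and flyer carry it. If they do not, state whether non-smokers may enter.

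Whatever the recruitment status, report baseline HIV and smoking status for everyone enrolled in the study proper. This can be done after enrolment has ended and needs no change to the intervention or the analysis models.

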Importance of the Problem to Be Addressed. The proposed pilot study seeks to explore modulation of attentional bias and tobacco craving in PLWHA with one session of adequately dosed theta burst stimulation (TBS). Results of this trial will spur clinical research to further investigate the use of TBS as an adjunctive smoking cessation aid for PLWHA and could have broad implications for smoking cessation programs. Data obtained from this pilot study will also facilitate resubmission of a grant application examining adjunctive theta burst stimulation (TBS) combined with varenicline for smoking cessation in PLWHA. People living with HIV/AIDS (PLWHA) smoke at nearly three times the rate of the general population (1-7). These extraordinary smoking rates are associated with greater AIDS-related morbidity (8-10), non-AIDS related morbidity including non-AIDS-defining cancer, cardiovascular disease, pulmonary disease (11-18), and mortality (19-22). Smoking significantly impacts the progression and outcome of HIV disease and has been identified as the leading contributor to premature mortality in PLWHA (23). One study estimated PLWHA lose more years from smoking than from HIV infection (21). In our view, shared by others in the field, the single greatest health behavior change that could improve mortality is to assist smokers living with HIV/AIDS to quit smoking (23-30).

Pharmacotherapies for Smoking Cessation in PLWHA. Trials involving use of nicotine replacement therapy (NRT) have shown no effect on cessation rates when used alone (31, 32) and mild efficacy when used in combination with behavioral therapies in PLWHA (33-35). Adherence to NRT was also low (34). No controlled trials have compared NRT with other smoking cessation interventions in PLWHA (36). Although bupropion has been approved for smoking cessation in healthy adults, no randomized trials have explicitly examined the efficacy of bupropion for smoking cessation in PLWHA (36). There have also been concerns regarding interactions between bupropion and antiretroviral therapy (HAART)(37, 38). Varenicline is considered the most effective pharmacologic agent available for smoking cessation (39). There are no reported pharmacodynamic interactions between varenicline and HAART (37, 40). Varenicline was found to be safe and well tolerated for smoking cessation interventions among PLWHA (40-42). It showed higher continuous abstinence rates (OR=4.65, CI 1.71-12.67, p=0.003) compared to placebo during weeks 9-12 (43), when dosed for 12 weeks. In another trial combining varenicline and NRT resulted in significantly higher continuous abstinence at weeks 12 (OR=1.85, p=0.007) and 24 (OR=1.98, p=0.004) (44). Despite these results, suboptimal adherence to varenicline poses a significant barrier resulting in lower quit rates in community studies compared to clinical trials (45). The extant literature suggests the efficacy of pharmacotherapeutics prescribed as smoking cessation aids is suboptimal in smokers in general and PLWHA in particular (30, 36). These findings along with high smoking rates in PLWHA underscore the urgent need to identify novel adjuncts to augment the efficacy and sustainability of commonly prescribed pharmacotherapies for smoking cessation.

Transcranial magnetic stimulation (TMS). TMS is a form of noninvasive brain stimulation. TMS uses a magnetic field to generate tiny modulated doses of electric current at a focal brain site, leading to neural changes and consequently changes in behavior and illness symptoms (46). In psychiatric illnesses like major depressive disorder (MDD) and schizophrenia, TMS has been used to augment medication treatments or treat residual symptoms, which are addressed sub-optimally by pharmacotherapy (47, 48). TMS has revolutionized the treatment of major depressive disorder (MDD), leading to FDA approval in 2008 for 10 Hz protocol. Neuroimaging studies have shown neural effects from TMS to result from activity modulation at stimulation site and downstream effects at other brain regions (49). These downstream effects result from connectivity changes in networks involving proximal cortical stimulation target and distal network structures (49). TMS is safe and has been refined significantly over the last 20 years.

The neurobiology of nicotine addiction encompasses increased dopaminergic activity in the mesolimbic reward pathway (nucleus accumbens and ventral tegmental area), via removal of inhibitory GABAergic activity (50). TMS at the left dorsolateral prefrontal cortex (DLPFC) causes increased dopaminergic release at the site of application and downstream dopaminergic modulation in the reward pathway, consequently leading to reduced craving (51). A recent meta-analysis showed excitatory TMS to the left dorsolateral prefrontal cortex (DLPFC) showed a medium effect size for craving reduction for nicotine (Hedges' g 0.471, CI 0.820 to 0.122, $p=0.008$) (52). Importantly, across substances, including nicotine, number of stimulation pulses predicted the effect size for reductions in craving (52). TMS has been used for smoking cessation in a few clinical studies with otherwise healthy individuals (53). Ten previous studies have applied excitatory TMS (10-20 Hz), one study applied inhibitory TMS (1 Hz) and one previous study applied TBS to reduce craving for cigarettes in subjects with no comorbid psychiatric diagnoses (53). Number of sessions ranged from one to ten, with four being median (53). Eight studies targeted left or right DLPFC, one used an H coil targeting bilateral DLPFC and insula (54) and one study targeted the left superior frontal gyrus (55). Nine out of ten studies used craving measures as outcomes, all assessed abstinence from smoking cigarettes at various time points. All these have been pilot studies, with sample sizes ranging from 16 to 48.

Theta burst stimulation (TBS). A new TMS paradigm, theta burst stimulation (TBS), uses theta frequency stimulation at gamma frequency. TBS is different from other TMS frequencies in that it delivers significantly more dosing pulses over the same time period. TBS is safe and was approved for MDD by the FDA in 2019. To the best of our knowledge, there has been only a single clinical study that utilized theta burst stimulation for smoking cessation. Four sessions of intermittent TBS (iTBS) added to Cognitive Behavioral Therapy (CBT, twice weekly sessions for three weeks) (56) were delivered. Participants (N=74) received either iTBS (600 pulses) or sham TMS. The groups did not differ in number of cigarettes smoked or scores on Fagerstrom Test for Nicotine Dependence (FTND). At three months of follow-up, the iTBS group had 19 subjects reporting abstinence while 19 had relapsed. The sham TMS group had 10 subjects abstinent and 26 subjects who had relapsed. To the best of our knowledge, no studies used TBS or other rTMS for smoking cessation in PLWHA.

TMS for modulation of cognitive performance including attentional bias. TMS has also been used to modulate cognitive performance, to accelerate mechanisms of smoking cessation across various studies (57, 58). Previous TMS treatment studies for smoking cessation have included cognitive outcome measures including delayed discounting (59, 60) and cigarette cue induced craving assessed using an analogue scale (61). It is plausible modulation of these cognitive paradigms by TMS could contribute to craving reduction and behavioral changes in cigarette use. Multiple previous studies support the existence of an attentional bias towards smoking related cues compared to neutral cues in tobacco use disorder(62). Modulation of attentional bias has been attempted in MDD. To the best of our knowledge, no study has used TMS to modulate attentional bias in subjects with smoking behavior.

Stress induced craving paradigm. The pathophysiology of nicotine dependence includes the interaction between stress, environment and body physiology, fuelling the illness(63). Multiple previous studies have modeled craving for nicotine in the presence of stress, to approximate real world scenarios(64-66). Before we test TBS as a clinical intervention, we will explore whether one session of TBS can modulate craving in the context of induced stress. Two promising paradigms for stress induction are the cold pressor test (CPT) wherein participants immerse their feet in ice cold water (2-4 degree Celsius) for three minutes and the paced serial addition task (PASAT)(67). The cold pressor test invokes an immediate cardiovascular stress response, initiated by the sympathetic nervous system, followed by a neuroendocrine response controlled by the hypothalamus-pituitary-adrenal (HPA) axis(67). The PASAT is a cognitively challenging task and will be performed in parallel with the CPT as an additional means for stress induction. The task requires participants to listen to a standardized audio-recording of a series of single-digit numbers and to say aloud the sum of the last two numbers presented (within each inter-trial interval). The PASAT will also last less than three minutes. Peak stress response occurred 20 minutes after these paradigms were performed(67). In our pilot study, these paradigms will be performed simultaneously, and followed by the tobacco craving questionnaire (TCQ).

Brain network connectivity to complement attentional bias modulation. Neuroimaging has shown resting state functional connectivity (rsFC) changes in patients who smoke(68). This encompasses connectivity changes in default mode network, executive control network and salience network. Previous studies have shown a negative correlation between smoking behavior severity and connectivity in the dorsal anterior cingulate (dACC)- ventral striatum (VS) circuit(68). Previous studies have also shown the salience network to be deeply involved in the regulation of attention to smoking cues versus neutral cues(68). Given that neuroimaging could potentially corroborate attentional bias modulation with TBS, we will attempt to explore correlations between changes in attentional bias and salience network as well as between changes in stress induced craving and connectivity in the dACC-VS circuit.

References

